Protocol

1. Title:

Assessing Efficacy of Intramuscular Promethazine for the Treatment of Intrathecal Morphine Induced Pruritus

Version 2.0

Date April 22, 20225

2. Investigators

Principal Investigator: [name]

Co-Investigators: [name]
[name]
[name]
[name] [name]
[name]
[name], MA

Study Coordinators: [name]

3. Abstract:

This study aims to analyze a novel approach for prophylaxis against pruritis caused by neuraxial narcotics. Neuraxial narcotics are commonly used in obstetric patients for cesarean delivery to help with pain control over the first 24 hours after the surgery. Slappendel demonstrated intramuscular promethazine (IMP) was an effective treatment for intrathecal morphine induced pruritis (ITMIP).¹ No other studies evaluated IMP for treatment of ITMIP. The primary aim of this study will be to evaluate effectiveness of IMP prophylaxis of ITMIP. Finding a prophylaxis for ITMIP other than naloxone, will allow for increased use of intrathecal narcotics and potentially decrease the use of systemic opioids in the initial post-operative period.

This study will use in-patients undergoing cesarean delivery at UF Health Shands Hospital in Gainesville, Florida.

4. Background and Significance:

Intrathecal morphine given during cesarean deliveries is one of the many ways providers currently help post-partum women with pain control. One major downside of intrathecal morphine is pruritus that occurs over the next 24-48 hours. During this time the mother should be enjoying time with her new infant, but instead is having to deal with the itching from the pain reliever we have given her. The

cause for the pruritus is not well known, but what is known is that anti-histamines such as diphenhydramine do not work. One class of medications known to help decrease ITMIP include mu opioid antagonists such as naloxone but some suggest there may be decreased analgesia when mu opioid antagonists are utilized. Further, due to the short half-life of naloxone, infusions of the medication must be used to adequately prevent recrudescence of symptoms in the setting of ITMIP. The related medication, nalbuphine, a partial opioid agonist has been found to be effective at treating ITMIP at the expense of increasing sedation and possibly nausea.²⁻⁵ Nausea and vomiting is a frequent complication during cesarean delivery.

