Hypothesis: Prophylactic intramuscular promethazine does not decrease pruritus in post-partum females that received 100mcg intrathecal morphine.

Alternate Hypothesis: Prophylactic intramuscular promethazine does decrease pruritus in post-partum females that received 100mcg intrathecal morphine.

Pruritus will be quantified by the ItchyQuant Scale, developed and validated by CG Haydek as seen below.⁹

Secondary Analysis

- Promethazine does not increase sedation compared to placebo (RASS scale)
- Promethazine does not increase pain compared to placebo (DVPRS scale)
- Promethazine decreases nausea and vomiting (rated as none, mild, moderate, severe)

6. Research Plan:

Inclusion criteria:

1. Pregnant adult female patients of at least 18 years of age consenting to a cesarean birth;
2. Willing to consent to study.

Exclusion criteria:

1. Male patients;
2. Incarceration;
3. Inability to communicate with the investigators;
4. Allergies to any medications used in the study;
5. Possessing any contraindication to spinal anesthesia (lack of consent, elevated intracranial pressure, preexisting neurological disease, thrombocytopenia/coagulopathy, hypovolemia, infection at the site of the procedure);
6. Patients with an already prolonged QTc (>500 ms)
7. Any reason an investigator believes study participation would not be in the best interest of the potential subject.

DESIGN

STUDY PROCEDURES

Recruitment

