The patient will come to the obstetric (OB) pre-operative holding area where we will obtain her medical history, perform a physical exam and consent her for the cesarean delivery. The patient will have already spoken with a study coordinator and/or PI/Co-I more than one day prior to arrival regarding potential participation in the study. The patient will be approached by one of the study team members (anesthesiologists). We will review the consent form, explaining that itching is a common side effect of the intrathecal morphine and we are trialing a medication that would prevent the itching. If the patient agrees to participate, we will obtain signed consent, contact the study coordinator to be prepared for questionnaires post-procedure and then obtain a blinded syringe from pharmacy for the treatment. [name] will randomize the patient for the study to determine which medication the mother will receive using a stratified randomization design generated with MAPLE software.

The patient will then go back to the operating room when it is her operative time, and we will perform the spinal with bupivacaine, morphine and fentanyl, which is standard at our institution (see standard of care medications below). Once the spinal is confirmed to be adequate, the surgical team will be called in to perform the procedure. Once the baby is delivered and the procedure is completed, we will inject the blinded syringe of medication into the patient's left thigh since she will still be numb from the spinal. When the patient arrives to the PACU, we will assess the 4 variables 1 hour after medication is given in PACU and then between 4-5 hours post-op and at 24 hours post-op (+/- 2 hours). All evaluations will be done in person or by phone call from study coordinator.

If patients are still reporting pruritis that is not controlled, the rescue treatment will be butorphanol 1mg IV q3h, as this is the current regimen at our institution.

Treatment/Therapy

The treatment will consist of a blinded syringe of 1cc clear liquid (blinded to patient and physician – only pharmacist will know what it contains). This injection will be given in the left thigh after the cesarean delivery is completed.

Contents of syringe: (either)

- 1cc 0.9% Sodium Chloride (placebo)
- 1cc 25mg/ml Promethazine (study medication)

Extra studies/procedures required

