It is standard of care for all patients for this surgery to have intraoperative 5 lead EKG monitoring. All study patients will have QTc evaluated on the anesthesia monitor. As part of the study, rhythm strips will be printed out and saved in study binder. Any patients with an already prolonged QTc (>500 ms) will be excluded from the study.

Recording data responsibilities

1. Anesthesia attending on OB for the day will consent patient if they agree to the study.
2. [name] team will perform randomization.
3. Study coordinator will be contacted once patient is enrolled.
4. Time 0 will be recorded by resident/attending in the room at the time the medication is given.
5. Study coordinator will contact patient in person or by phone at 1 hour, 4-5 hours , and 24 (+/- 2 hours) hours to assess given variables.

Drugs that will be given as STANDARD OF CARE during the study will be:

1: Bupivacaine 0.75% 1.4-2.0 IT (Spinal anesthetic)

2: Fentanyl 20 mcg IT (Spinal anesthetic)

3: Preservative Free Morphine 100 mcg IT (Spinal anesthetic)

4: Butorphanol 1mg IV every 3 hours (rescue treatment)

5: Nalbuphine 2.5mg IV every 6 hours as needed for itching

6: Ondansetron 4mg IV every 6 hours as needed for nausea

7: Ketorolac 30mg IV once

8: Acetaminophen 975mg by mouth every 6 hours (scheduled)

9: Phenylephrine 100-200mcg as needed every 2 min and phenylephrine infusion 0.1 mcg/kg/min IV titrated to maintain maternal BP within 20% of baseline.

10: Ephedrine 5-10mg IV as needed every 2 min to maintain maternal BP within 20% of baseline, secondary agent to phenylephrine bolus and infusion and/or if maternal HR falls below 70 bpm.

11: Cefazolin 2g IV once before incision

12: Azithromycin 500mg IV once before incision

13: Clonidine 15-30mcg IT (Spinal anesthetic)

If penicillin allergic (given as STANDARD OF CARE):

1: Clindamycin 900mg IV once before incision

2: Gentamicin 1.5mg/kg IV once before incision

Drugs that will be given as part of the study:

1: Intramuscular Promethazine 25mg (25mg/mL)
2: Intramuscular 0.9% Sodium Chloride (placebo, also 1mL)

Table of Study Events

| Activity | Time Point | Time Point | Time Point | Time Point |
|--|------------|------------|------------|------------|
| Injection of blinded medication | 0 | | | |
| First Evaluation of variables (Phone call from coordinator) | | 1 h | | |
| Second Evaluation of variables (Phone call from coordinator) | | | 4-5 h | |

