| Final Evaluation of variables (Phone call from coordinator) | | | | 24 h |

STATISTICAL METHODS, DATA ANALYSIS, AND INTERPRETATION:

Our plan is to recruit 50 patients for each arm of the study. With 50 patients on placebo and 50 patients on Phenergan, there will be a greater than 80% chance of detecting a significant difference of 20% or more at a two-sided 0.05 significance level. This assumes that severe itching occurs in 50% of patients and Phenergan reduces this proportion to 20%.

We will use Fisher's exact test to compare groups on severity of itching. We will also use Wilcoxon's rank sum test to compare groups on degree of itching as measured by the ITCHYQUANT. [name], the study biostatistician, will perform all statistical analyses.

DATA STORAGE AND DE-IDENTIFICATION PLANS:

The original, hard-copy signed informed consent forms and rhythm strips will be stored within the locked Anesthesiology research office and will remain with the Principal Investigator for at least 7 years. Data will be entered into an Excel spreadsheet kept on a password-protected and encrypted computer and retained by the Principal Investigator for at least 7 years.

Patients will be de-identified. No names, MRN's, or other identifying information will be stored in the spreadsheet. Pain, itching, sedation and nausea/vomiting will be collected at three intervals by a study coordinator and added to the de-identified spreadsheet. Age group, medical conditions such as diabetes and pre-eclampsia as well as BMI groups, will be used to determine confounders in the data. None of this collected information will be used to identify the patients.

7. Potential Risks:

Subjects will be given clear verbal and written instructions to contact [name] in the Department of Anesthesiology with questions or concerns regarding their study participation. If a patient experiences an injury that is directly caused by this study, they will receive professional medical care at the University of Florida. No other compensation is offered. Any adverse events will be reported to the

IRB using the standard adverse events reporting website and on continuing reviews (depending upon severity, as defined by the IRB).

1. Sedation (study variable). Promethazine can cause sedation which will be studied.
2. Concern for QT prolongation on the ECG causing cardiac arrhythmias. QTc evaluated on patient monitor, rhythm strip to be printed off and saved in research binder with QTc labeled clearly.

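### Itch is not scored just before the injection, so the trial cannot tell prevention of new itch from relief of itch already present, and cannot adjust for the baseline value

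*Combined protocol and SAP*

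**What the plan says.** The Abstract (section 3) gives the purpose: "The primary aim of this study will be to evaluate effectiveness of IMP prophylaxis of ITMIP". The alternate hypothesis in section 5 has the same framing: "Prophylactic intramuscular promethazine does decrease pruritus in post-partum females that received 100mcg intrathecal morphine". The title speaks of treatment.

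Section 6, under the heading on the patient's typical day, sets the order of events. Before the operation, "we will perform the spinal with bupivacaine, morphine and fentanyl". Afterwards, "Once the baby is delivered and the procedure is completed, we will inject the blinded syringe of medication". The first rating follows: "When the patient arrives to the PACU, we will assess the 4 variables 1 hour after medication is given in PACU".

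The list of recording responsibilities gives the full schedule: "Study coordinator will contact patient in person or by phone at 1 hour, 4-5 hours , and 24 (+/- 2 hours) hours". At the injection itself only the time is noted: "Time 0 will be recorded by resident/attending in the room at the time the medication is given". The data storage paragraph confirms the count: "Pain, itching, sedation and nausea/vomiting will be collected at three intervals by a study coordinator". The table of study events shows nothing but the injection at time 0.

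No eligibility criterion concerns existing itch. The candidate confounders are age group, medical conditions and BMI group. The planned itch analyses are Fisher's exact test and Wilcoxon's rank sum test, both unadjusted.

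**The concern.** The spinal opioids have been acting for a whole operation when the study drug is given. Some women may already itch at Time 0, or be nauseated, sedated or in pain. Under the present schedule a woman who was itching at the injection and one whose itch began afterwards look the same at one hour.

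Two things are at stake. The first is interpretation. A benefit could be prevention, relief of existing itch, or a mixture. A null result could be failed prevention, or could arise partly because itch had already begun. The background in section 4 treats prevention and treatment as separate bodies of evidence with conflicting results, so the distinction matters to the trial's purpose. The second is precision: a pre-injection value of the outcome is a natural adjustment variable, and here it does not exist. Neither loss can be recovered after the trial.

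**Working it through.** **Order of events in section 6**

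| Event | When | Itch scored? |
|---|---|---|
| Spinal with morphine and fentanyl | Before surgery | No |
| Blinded injection (Time 0) | After the procedure is completed | No, clock time only |
| First rating | 1 h | Yes |
| Second rating | 4-5 h | Yes |
| Final rating | 24 h (± 2 h) | Yes |

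All three ratings come after the injection.

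**The plan's own power figure.** Inputs from the statistical section: 50 per arm, two-sided 0.05, severe itching 50% against 20%. Exact power of Fisher's test, by enumerating all outcomes, is 85.3%; the pooled normal approximation gives 89.4%. The stated figure of more than 80% therefore holds for these rates. A Time-0 score leaves this all-patient, unadjusted test, and so its power, unchanged.

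**What adjustment could gain.** The documents give no standard deviation for the ItchyQuant and no correlation between a Time-0 score and later scores. Both inputs are therefore assumptions: a standardised difference of 0.5, and a range for r. Adjusting a continuous score for a baseline with correlation r leaves a share 1 − r² of the variance. The effective standardised difference is 0.5/√(1 − r²), and the effective total sample size is 100/(1 − r²). Power is from the two-sided two-sample t-test (noncentral t, 98 degrees of freedom), with noncentrality equal to the effective difference × √(50/2):

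| r | 1 − r² | Effective difference | Noncentrality | 100 patients work like | Power |
|---|---|---|---|---|---|
| 0 | 1.00 | 0.500 | 2.500 | 100 | 69.7% |
| 0.1 | 0.99 | 0.503 | 2.513 | 101 | 70.1% |
| 0.3 | 0.91 | 0.524 | 2.621 | 110 | 73.7% |
| 0.5 | 0.75 | 0.577 | 2.887 | 133 | 81.6% |

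The t-test stands in for the rank-based analysis as an approximation, and the formula does not carry over directly to the binary severe-itch outcome. If few women itch at the end of surgery, r could be near zero and the gain negligible. The interpretive gap does not depend on r.

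**The case against.** The strongest reply is that the planned comparison already answers a legitimate question. The hypothesis is about decreasing pruritus in women who received intrathecal morphine and does not limit itself to new-onset itch. Prophylactic can mean a routine injection for every woman at the end of surgery, with itch then compared over 24 hours. Post-injection scores in randomised arms answer that without bias, and a null result would still show that the routine injection did not beat saline. All of this stands. It is why the all-randomised comparison should remain the main result, and why it would be too strong to say that a null result cannot be read. What remains is that the data could not show how far any effect was prevention.

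A reader might also infer that the missing score costs the trial much of its power. Suppose 10%, 20% or 40% of would-be severe cases already itch at the injection and get no benefit. The promethazine rate becomes 0.5 × (f + (1 − f) × 0.4), that is 23%, 26% or 32%, and Fisher power falls from 85.3% to 75.3%, 63.4% or 38.2%. The documents do not support charging that loss to this omission:

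- It would come from injecting after surgery, and recording a score would not restore it in the planned test.
- The shares are invented; no document says how many women itch at the end of surgery.
- Zero benefit in women already itching sits badly with section 4, which reports an unblinded study in which only one of 143 patients needed more than intramuscular promethazine.

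Finally, extra analyses add to a plan that already has two tests and three time points. That is fair, and it is met by labelling the new-onset result as secondary in advance.

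**Conclusion.** The concern holds as one of interpretation and precision. All ratings follow the injection, the opioids precede it by a whole operation, and the stated aim is prophylaxis, so prevention of new itch and relief of existing itch cannot be told apart. The randomised comparison remains valid.

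The precision gain is uncertain: from under half a percentage point of power (r = 0.1) to about 12 points (r = 0.5), on the assumed standardised difference of 0.5 and for a continuous score only. No loss of Fisher power should be attributed to the missing score. This is a cheap improvement worth making before enrolment, because the measurement cannot be reconstructed later.

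**What to change.** Just before the blinded injection, have the resident or attending who already records Time 0 also record the ItchyQuant and the ratings for pain, sedation and nausea/vomiting. Add the row to the table of study events. Although this falls after randomisation, it precedes the study drug and the syringe is blinded, so treatment cannot affect the score. Exclude no one on the basis of it.

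In the statistical section:

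- Keep the comparison of all randomised women as the main result.
- Adjust the ItchyQuant comparison for the Time-0 score, by rank-based ANCOVA or a proportional-odds model.
- Prespecify new-onset itch among women with no itch at Time 0 as a secondary analysis that does not displace the main result.
- State how a missing Time-0 score will be handled, so that no woman drops out of the main comparison because of it.

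The cost is about a minute per patient and one extra row on the data sheet, with no extra visit, staff or procedure. The drawback is that a score taken in the operating room will occasionally be missing.

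### As-needed ondansetron is neither recorded nor analysed, so a null result on the nausea and vomiting hypothesis could not be told apart from a benefit masked by rescue

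*Combined protocol and SAP*

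**What the plan says.** Section 5 (Specific Aims, Secondary Analysis) states a directional hypothesis on a four-level scale: "Promethazine decreases nausea and vomiting (rated as none, mild, moderate, severe".

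Section 6 lists the standard-of-care drugs for all participants, among them "Ondansetron 4mg IV every 6 hours as needed for nausea". The timing of the ratings is under Recording data responsibilities: "Study coordinator will contact patient in person or by phone at 1 hour, 4-5 hours , and 24 (+/- 2 hours) hours to assess given variables". Time 0 is the study injection, given after the cesarean is completed.

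The section on data storage and de-identification describes what is entered: "Pain, itching, sedation and nausea/vomiting will be collected at three intervals by a study coordinator and added to the de-identified spreadsheet". The only other variables named are covariates: "Age group, medical conditions such as diabetes and pre-eclampsia as well as BMI groups, will be used to determine confounders in the data". Antiemetic use appears in neither sentence, and no other section says how it is recorded or handled.

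The statistical section names tests for itching only. It says "We will use Fisher's exact test to compare groups on severity of itching" and adds a Wilcoxon rank sum test on the ItchyQuant score. It names no test for nausea and vomiting, and the protocol does not say whether the rating is of current symptoms or of the worst since the last contact.

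**The concern.** Ondansetron on demand is given because of the very symptom the hypothesis concerns, and it is given after allocation, so randomisation does not balance it. If promethazine works as hypothesised, more placebo women become nauseated and more are treated. A rating of current symptoms at the next contact then describes treated nausea. Part of the benefit moves out of the rating and into ondansetron use, which the plan does not collect.

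At stake is the reading of a null result. With ratings alone, the trial could not say whether promethazine has no antiemetic effect or has one that rescue concealed. The gap between the second and third contacts is about 19-20 h at nominal times, which leaves ample room for unrecorded doses.

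**Working it through.** **1. The plan's own figure.** The only power statement concerns severe itching, 50% vs 20%: "Our plan is to recruit 50 patients for each arm of the study", with a "greater than 80% chance of detecting a significant difference of 20% or more at a two-sided 0.05 significance level". At 50 per arm the normal approximation gives 89.4% and exact enumeration of the two-sided Fisher test gives 85.3%. The stated power for 50% vs 20% therefore reproduces. Nothing comparable is stated for nausea.

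**2. Inputs for the nausea illustration.** From the documents: 50 per arm and two-sided 0.05. Assumed, because the documents are silent: the true nausea rates, the share of nauseated women given ondansetron before the rating (use), the share of those whose nausea has cleared by the rating (clearance), a rating of current symptoms, and a yes/no reading of the rating tested by Fisher's exact test.

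**3. Formula.** Observed rate = true rate × (1 − use × clearance).

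**4. Assumed true rates 50% vs 25%, same use and clearance in both arms.**

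| Use × clearance | Observed, placebo vs promethazine | Difference | Exact Fisher power |
|---|---|---|---|
| 0 | 50% vs 25% | 25 points | 67.5% |
| 0.50 × 0.50 = 0.25 | 37.5% vs 18.75% | 18.75 points | 47.6% |
| 0.50 × 0.80 = 0.40 | 30% vs 15% | 15 points | 35.4% |
| 0.80 × 0.80 = 0.64 | 18% vs 9% | 9 points | 16.5% |

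**5. Other assumed rates, with 0, 25, 50 and 75% of cases resolved equally in both arms.**

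- 50% vs 30%: difference 20, 15, 10, 5 points; Fisher power 46, 30, 17, 6%.
- 50% vs 20%: difference 30, 22.5, 15, 7.5 points; Fisher power 85, 67, 41, 14%.

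**6. Unequal resolution, true 50% vs 30%.**

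- 50% of placebo and 25% of promethazine cases resolved: 0.50 × 0.50 = 25% vs 0.30 × 0.75 = 22.5%, a difference of 2.5 points with Fisher power 3.7%.
- The reverse (25% and 50%): 0.50 × 0.75 = 37.5% vs 0.30 × 0.50 = 15%, a difference of 22.5 points, slightly more than the true 20.

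Shrinkage thus follows when rescue resolves an equal or larger share of placebo cases. It is not a mathematical certainty.

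**7. No true effect.** The Fisher test rejects in 3.1% of trials at 30% vs 30% and in 2.4% at 15% vs 15%. Equal rescue does not inflate false positives.

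**8. Counting rescue as an event.** If ondansetron is given only to women with nausea, an outcome of symptoms or ondansetron use restores the unmasked rates, that is, the first row of the table.

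**The case against.** Five points can fairly be made against this concern.

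- **Target of estimation.** Comparing the arms under usual care, with antiemetic available to both, is a legitimate question, and relative to that target nothing is biased. This stands as a principle. But the protocol does not declare that target, and without usage data even that comparison is hard to interpret when it is null.
- **Direction.** A reader might infer that the nausea comparison as a whole is biased towards no difference. The documents do not support that. Section 4 notes that nalbuphine possibly increases nausea, and Section 6 offers it as needed for itching. If promethazine prevents itch, placebo women may receive more nalbuphine, which could raise their nausea and widen the difference. Only the ondansetron pathway has the stated direction; the net direction is unknown.
- **Snapshot.** A reader might also infer that treated nausea necessarily escapes the rating. That holds only for a rating of current symptoms. A rating of the worst since the last contact would still capture much of it. The protocol defines neither, so the undefined recall window is part of the gap.
- **Test and power.** No test is named for nausea, so the Fisher figures describe an analysis that the protocol does not contain. Under the assumed 50% vs 25%, power is only 67.5% without any rescue, so part of the risk of missing a benefit exists regardless. With equal resolution in both arms, the risk ratio also stays at 0.5 throughout; what is lost is absolute difference and power. All of this stands.
- **Weight.** This is one of three secondary hypotheses. That limits its importance but does not remove the defect.

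**Conclusion.** The concern holds in a limited form. A stated secondary hypothesis rests on a rating that as-needed treatment for the same symptom can alter, and that treatment is neither among the collected data nor in any analysis rule. If promethazine reduces nausea and the rating reflects current symptoms, ondansetron will tend to shrink the observed difference, and a null result would be uninterpretable.

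The size cannot be derived from the documents. Under the main illustration (50% vs 25%, equal use and clearance in the arms), the difference falls from 25 points to between 18.75 and 9, and power from 67.5% to between 47.6% and 16.5%. These figures show how strongly the result depends on rescue; they are not estimates for this trial. The primary itch analysis is unaffected by this point. It should be corrected because the data are cheap to collect and the de-identified spreadsheet cannot supply them later if they were never entered.

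**What to change.** 1. Copy the dose and time of each ondansetron administration after Time 0 from the medication record into the spreadsheet. Doses given before the injection cannot be an effect of the study drug and should not count.
2. Define the rating as the worst nausea or vomiting since the previous contact, and since the injection for the 1 h contact.
3. In the statistical section, compare by arm (a) the proportion with any post-injection ondansetron and (b) a 24 h binary outcome of moderate or severe nausea, vomiting, or any post-injection ondansetron. Report the raw rating beside both.
4. Optionally, add a sensitivity analysis that ranks ondansetron use with the worst category. It should not be the main analysis, because it would score a single dose for mild nausea as severe.

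The cost is one chart item per patient and a few sentences. The small downside is that the composite mixes symptoms with drug use, which is why its components and the raw rating should be shown with it. This concerns recording and analysis only; antiemetic care does not change.

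### The claim of more than 80% power is attached to a 20% difference, but 50 per arm gives that power only for the assumed 30-point fall (50% to 20%); for 20 points it is about 46%

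*Combined protocol and SAP*

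**What the plan says.** The power statement is in protocol section 6 (Research Plan), under Statistical Methods, Data Analysis, and Interpretation. It has four parts:

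- Sample size: "Our plan is to recruit 50 patients for each arm of the study".
- Power claim: a "greater than 80% chance of detecting a significant difference of 20% or more at a two-sided 0.05 significance level".
- Rates behind the claim: "This assumes that severe itching occurs in 50% of patients and Phenergan reduces this proportion to 20" (per cent).
- Test for the binary outcome: "We will use Fisher's exact test to compare groups on severity of itching".

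No other section restates or corrects the effect size, and no allowance for dropout is given.

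**The concern.** The two sentences give different effect sizes for one power claim. The assumed rates differ by 50 − 20 = 30 points, or 30/50 = 60% in relative terms. Neither scale gives 20%. Adding 'or more' makes 20% read as the smallest difference that the trial can reliably detect.

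This is the document's only power statement. A reader who takes 20 points as the detectable effect would think the trial has less than a one-in-five chance of missing it, when it would miss it more often than not. That affects how a non-significant result is read. Section 8 (Potential Benefits) also ties follow-on research to whether the hypothesis is rejected.

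**Working it through.** **Inputs**, all from the same subsection: n = 50 per arm, 1:1 allocation, two-sided α = 0.05, placebo rate 50%, promethazine rate 20%, Fisher's exact test.

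**Method.** Exact power is the sum, over all 51 × 51 possible outcomes (a, b), of

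Bin(a; 50, p₁) × Bin(b; 50, p₂), counted where the two-sided Fisher p-value is ≤ 0.05.

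As a hand check, the pooled normal approximation is

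power = Φ[(d − 1.96·SE₀)/SE₁], with d = p₁ − p₂, p̄ = (p₁ + p₂)/2, SE₀ = √(2p̄(1 − p̄)/50) and SE₁ = √((p₁(1 − p₁) + p₂(1 − p₂))/50).

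**Step 1: the plan's own figure (50% versus 20%).**

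- p̄ = 0.35, SE₀ = √0.0091 = 0.0954, SE₁ = √0.0082 = 0.0906.
- (0.30 − 1.96 × 0.0954)/0.0906 ≈ 1.25, so power ≈ 0.894.
- Fisher exact power is 0.8527.

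The claim of more than 80% reproduces for a 30-point difference.

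**Step 2: the difference named in the claim, in absolute points (50% versus 30%).**

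- p̄ = 0.40, SE₀ = √0.0096 = 0.0980, SE₁ = √0.0092 = 0.0959.
- (0.20 − 1.96 × 0.0980)/0.0959 ≈ 0.08, so power ≈ 0.533.
- Fisher exact power is 0.4635.

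**Step 3: the same 20% read as a relative reduction (50% versus 40%).** The pooled approximation gives 0.169 and Fisher 0.134.

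| True rates | Difference | Fisher exact | Pooled normal |
|---|---|---|---|
| 50% vs 20% | 30 points | 0.853 | 0.894 |
| 50% vs 21% | 29 points | 0.822 | 0.869 |
| 50% vs 22% | 28 points | 0.789 | 0.841 |
| 50% vs 30% | 20 points | 0.4635 | 0.533 |
| 50% vs 40% | 10 points (20% relative) | 0.134 | 0.169 |

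**Step 4: smallest detectable fall from 50%.** Fisher power equals 0.80 at p₂ = 0.2168, a difference of 0.50 − 0.2168 = 0.283. That is 28.3 points, or 29 in whole points.

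**Step 5: does the choice of method matter?** For 50% versus 30%, the unpooled normal approximation gives 0.550, an uncorrected chi-square by the same enumeration 0.5455, and a continuity-corrected formula 0.450. A one-sided 0.05 test gives 0.573 (Fisher) or 0.657 (pooled). None reaches 0.80.

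**Step 6: sample size for 20 points.** For 50% versus 30% at 80% power, the uncorrected formula gives 93 per arm and the continuity-corrected formula 103. Fisher exact power is 0.751 at 93 per arm, 0.792 at 100 and 0.811 at 103.

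**Step 7: margin at the assumed rates.** For 50% versus 20%, Fisher power is 0.802 at 44 evaluable per arm and 0.796 at 43. The plan can therefore lose 50 − 44 = 6 patients per arm before power drops below 80%.

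**The case against.** The strongest defence is that the 20% refers to the observed difference. The plan gives the true rates separately, so the first sentence could describe the result the trial expects to see. On that reading the number is right: if the true rates are 50% and 20%, the chance of a significant result with an observed gap of at least 20 points is 0.8525. With 25/50 on placebo, a 20-point gap (25 versus 15) is also the smallest that an uncorrected chi-square calls significant (z = 0.20/0.0980 = 2.04, p about 0.04).

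This shows how the wording might have arisen, but it does not rescue it. The text does not say that the difference is an observed one, and a power statement is normally read as referring to a true difference. The extra condition does almost no work (0.8525 against 0.8527 without it). Under the planned Fisher test, 25 versus 15 is not significant (p = 0.066). The smallest significant gap at 25/50 is 22 points (25 versus 14, p = 0.040).

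A second defence is that a 20-point difference can have 80% power at another placebo rate. With 50 per arm and Fisher's test, that holds only for placebo rates of 23% or lower, or 97% or higher. The plan sets the rate at 50%.

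Two points on the other side do stand. The design rates appear in the very next sentence, so a careful reader can recover the 30 points. And 50 per arm is adequate for those rates, so nothing in the conduct of the trial has to change if 30 points is what was meant. The documents do not settle which difference was intended.

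**Conclusion.** The concern holds. As normally read, the power statement is wrong: with 50 per arm and Fisher's exact test at two-sided 0.05, power above 80% belongs to a fall from 50% to 20% (85.3%), not to a 20% difference (about 46% for 20 points, about 13% for a 20% relative reduction). The shortfall against the claimed 80% is about 34 points of power on the absolute scale.

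This rests on the plan's 50% placebo rate and on 50 evaluable patients in each arm. The conclusion does not depend on whether an exact or approximate method is used. It should be fixed, but it does not undermine the sample size for the rates assumed.

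**What to change.** Replace the two sentences with text such as:

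> With 50 evaluable patients per arm and Fisher's exact test at two-sided 0.05, power is about 85% for a reduction in severe itching from 50% to 20% (30 points). The smallest reduction from 50% detectable with 80% power is about 29 points. Power for a reduction from 50% to 30% (20 points) is about 46%.

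The sponsor should confirm that 30 points is the intended target. If so, the cost is two sentences and a less favourable stated figure, with enrolment, test and significance level unchanged. If 20 points was the target, rewording is not enough: about 103 per arm (206 in total instead of 100) would be needed before any allowance for dropout.
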